10.2 SAMPLE SIZE

The sample size estimate is based on attaining adequate power to test the primary hypothesis that at least 77% of participants will report subjective improvement in audio processor design with SONNET 3 (EAS) over the existing processor based on a single survey. The hypothesis test is a one-sample, one-sided test of the proportion of participants reporting an average score of >3 on the Audio Processor Comparison Survey (APCS) compared to 77%, based on the clinical trial for the Cochlear Nucleus 7 audio processor, where an average of 77% of participants responded with greater than neutral agreement (>50 on a 100-point scale) on survey questions addressing satisfaction with improved comfort with the new audio processor. For the purpose of this sample size calculation, 77% will represent the desired participant response proportion.

A power analysis was conducted using a binomial two-proportion test with the package 'pwr' in R. Using a 95% confidence interval, a sample size of 20 participants would provide 85% probability of rejecting the null hypothesis (H_0 : 77%). Calculations are based on the following assumptions:

- Hypothesized proportion: H_0 : $p < 0.77$;
- Expected proportion: H_1 : $p \geq 0.77$
- Significance level = 0.05
- One-sided
- Effect size $h=0.36$

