10.4 DESCRIPTION OF STATISTICAL METHODS

10.4.1 GENERAL APPROACH

Continuous variables will be summarized using mean, median, inter-quartile range, minimum, and maximum values. Categorical variables will be summarized using counts and percents. Testing of the primary endpoint will be done at the 0.05 level of significance.

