10.4.2 ANALYSIS OF THE PRIMARY EFFECTIVENESS ENDPOINT

The proportion of participants reporting design superiority with SONNET 3 (EAS) on the APCS will be calculated for the primary endpoint. The participant's responses to the Design subsection questions will be averaged and the proportion of participants who rated >3 on average will be compared to the hypothesized proportion of 77%. The statistical hypothesis for the primary endpoint is defined as:

$$H_0: p < 0.77$$

$$H_1: p \geq 0.77$$

where p is the proportion of participants who responded with a mean score of >3.

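### The stated 85% power does not follow from the plan's own inputs: n=20, h=0.36 and one-sided alpha 0.05 give about 49% (39% exact), and a two-proportion test is named for a one-sample hypothesis

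*Combined protocol and SAP*

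**What the plan says.** Section 10.2 (Sample Size) defines the primary test: "The hypothesis test is a one-sample, one-sided test of the proportion of participants" whose mean score on the survey exceeds 3, against 77%. It then says: "A power analysis was conducted using a binomial two-proportion test with the package 'pwr' in R". The result claimed is that "a sample size of 20 participants would provide 85% probability of rejecting the null hypothesis".

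The listed assumptions include "Significance level = 0.05", a one-sided test and "Effect size $h=0.36". The hypotheses are H0: p < 0.77 and H1: p ≥ 0.77. No numerical alternative is given; the line for the expected proportion only repeats H1.

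Section 10.4.1 confirms the alpha: "Testing of the primary endpoint will be done at the 0.05 level of significance". Section 10.4.2 compares the observed proportion with the fixed value of 0.77 and does not say whether the test is exact or approximate. Section 4.1 describes a single-arm study of 20 participants.

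**The concern.** Sample size, alpha, sidedness and effect size together determine power, so the 85% can be checked directly. It looked too high: with 20 participants and a null as high as 0.77, an effect of h=0.36 is hard to detect. The method text also conflicts with itself, because a two-proportion calculation assumes a second sample that a single-arm comparison with a fixed value does not have. And because H1 is only a range starting at 0.77, the section never says at which true proportion the 85% is meant to apply. At the boundary of that range, power is no more than the size of the test.

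This calculation is the only justification for n=20 on the primary endpoint, which Section 4.1 presents as a demonstration of superiority. If power is well below 85%, a reader who trusts that figure would take a non-significant result as evidence against the device, when the study may simply have been too small to show an improvement of the assumed size.

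**Working it through.** **Inputs.** From Section 10.2: n = 20, one-sided alpha = 0.05 (z = 1.645), h = 0.36, null p0 = 0.77, claimed power 85%. Section 5.4.2 allows non-completers to be replaced, so 20 is taken as the evaluable number.

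**Implied alternative (derived, not stated in the plan).** h = 2·arcsin√p1 − 2·arcsin√p0. With p0 = 0.77 and h = 0.36, p1 = 0.901. As a check, p1 = 0.90 gives h = 2.498 − 2.141 = 0.357.

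**Attempts to reproduce the 85%.**

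1. One-sample arcsine power: Φ(h√n − z) = Φ(0.36·√20 − 1.645) = Φ(1.610 − 1.645) = **48.6%**.
2. Two-proportion arcsine power, the test named, with 20 per group: Φ(h√(n/2) − z) = Φ(0.36·√10 − 1.645) = Φ(1.138 − 1.645) = **30.6%**. With 10 per group it is 20.0%.
3. Exact one-sample binomial test, n = 20:

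| Reject if responders ≥ | Type I error at 0.77 | Power at 0.90 |
|---|---|---|
| 17 | 0.292 | 86.7% |
| 18 | 0.128 | 67.7% |
| 19 | 0.037 | **39.2%** |

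Only the 19-of-20 rule (or the stricter 20 of 20) keeps alpha at or below 0.05. At p1 = 0.901 its power is 39.7%.

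4. Other variants at alpha 0.05: two-sided one-sample arcsine 36.3%; score test about 36% (about 23% with continuity correction); z-test with null variance about 40%; z-test with alternative variance about 62%; effect taken downward (p1 = 0.604), exact, 38.8%.

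None of these comes near 85%. At n = 20 and h = 0.36, a power of 85% appears only if one-sided alpha is about 0.28 (arcsine); the 17-of-20 rule in the table shows the same thing.

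**What 85% would require.**

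- At h = 0.36, arcsine: n = ((1.645 + 1.036)/0.36)² = 55.5, so 56.
- At p1 = 0.90, exact: the first n to reach 85% is 60 (reject at 52 or more, power 85.8%). Exact power moves in a sawtooth: n = 61 to 64 give 84.8%, 83.7%, 82.5% and 81.3%, and n = 65 gives 88.9%.
- At n = 20, arcsine: h = 2.681/√20 = 0.60, a true proportion of 0.960.
- At n = 20, exact: P(X ≥ 19) is 73.6% at p = 0.95, 81.0% at 0.96, and reaches 85% at p = 0.9656.

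**The case against.** The strongest reply is that the arithmetic shows a conflict but not which number is at fault. With n = 20 and one-sided alpha 0.05, h = 0.60 gives 85.0% by the one-sample arcsine formula, so the power may be right and h misreported. The documents cannot settle this. It does not rescue the section: the listed inputs still do not give the stated power, and if h = 0.60 was meant, the plan assumes that about 96% of users will report improvement and does not say so.

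Two assumptions should be kept in view. The alternative of 0.90 is back-calculated from h. The 39% and the 19-of-20 rule assume an exact test, which the plan does not name. Neither affects the 48.6%, which uses h directly and the formula family that h belongs to.

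The endpoint wording in Sections 1.1, 3 and 10.1 could also be read as a criterion on the observed proportion, met by 16 of 20. That has a 95.7% chance of success at p = 0.90, again not 85%, and a 49.9% chance at p = 0.77. Sections 10.2, 10.4.1 and 10.4.2 specify a hypothesis test at the 0.05 level, so the testing reading is the stronger one.

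Finally, this is a low-risk survey study and the correction is to text. That limits the consequences for participants, but the figure is still wrong.

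**Conclusion.** The concern holds. The 85% in Section 10.2 is contradicted by the inputs listed beside it. Power at those inputs is 48.6% by the one-sample arcsine formula, 30.6% by the two-proportion test named, and 39.2% by an exact binomial test at p = 0.90. The shortfall is about 36 points (85 − 48.6) on the most favourable of these three and about 46 points (85 − 39.2) on the exact test. Rounding or the choice of approximation does not explain it.

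Taking h = 0.36 as the intended effect and the primary endpoint as a test at 0.05, the trial is more likely to miss than to meet its endpoint even if 90% of users prefer the new design: under the exact test, 18 responders of 20 would not reject. If h is the misreported figure, 85% holds only for a true proportion of about 0.96 or higher. Naming a two-proportion test for a one-sample hypothesis, and giving no numerical alternative, are separate defects in the same section.

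**What to change.** Reword Section 10.2, keeping n = 20:

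- Name a one-sample, one-sided exact binomial test of p = 0.77 at alpha 0.05, and use the same name in Section 10.4.2. State that 19 or more responders of 20 are needed to reject (actual type I error 0.037).
- Delete the reference to a two-proportion test.
- State the assumed alternative as a number. The sponsor should check the original calculation to see whether h = 0.36 or the 85% was misreported, and correct h to match.
- Replace the 85% claim with text such as: *With 20 participants, power is about 39% if the true proportion is 0.90, 74% if it is 0.95, and reaches 85% only at about 0.966.* These three figures serve whichever input was misreported.

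The cost is a change of wording and a less favourable power statement; no extra participants are needed. If the sponsor wants 85% power at about 0.90, that is a different decision. It would take about 56 participants by the arcsine formula or 60 by the exact test, with the exact power confirmed at the n chosen because of the sawtooth.

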10.3 ANALYSIS DATASETS

The intent-to-treat (ITT) population is defined as all enrolled participants including withdrawn participants who have been replaced. The modified ITT (mITT) population is defined as all participants who completed Visit 1 and Visit 2. The per protocol (PP) population is defined as participants who:

- Completed Visit 1 and Visit 2
- Were using the SONNET 3 (EAS) device consistently throughout the trial period
- Are free from major protocol deviations, including but not limited to:
 - Non-use of the SONNET 3 (EAS) during the trial
 - Missing test measures from one or more intervals
 - Evidence of not meeting inclusion/exclusion criteria after completion of study intervals

Analysis for the primary endpoint will be completed on the mITT and the PP populations.

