2.3 RISK/BENEFIT ASSESSMENT

2.3.1 KNOWN POTENTIAL RISKS

Any cochlear implant processor poses a risk of skin irritation or sensitivity to the processor materials. Materials in the SONNET 3 (EAS) (EAS) Audio Processor do not differ from those in the FDA-approved SONNET/SONNET 2 (EAS) Audio Processors. MED-EL has performed biological safety and compatibility testing with materials in the SONNET 3 (EAS) (EAS), and subjects with a skin or scalp condition that would preclude use of the audio processor will be excluded from this study. All cochlear implant processors and fitting software also pose a risk of overstimulation

and exposure to unwanted or uncomfortable sounds. The processor can be removed from the head at any time to immediately stop stimulation.

There is a remote chance that technical failure or suboptimal fitting of any audio processor leads to unwanted sensations, missing information, suboptimal hearing, or lack of benefit. Study participants who wish to stop using the SONNET 3 (EAS) (EAS) Audio Processor before study completion may withdraw from the study at any time and continue using their existing audio processor. Participants who experience poorer sound quality or performance with SONNET 3 (EAS) (EAS) may be reprogrammed after testing at Visit 2.

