5.4 PARTICIPANT WITHDRAWAL OR TERMINATION

5.4.1 REASONS FOR WITHDRAWAL OR TERMINATION

Participants or their parents/legal guardians may choose to withdraw from the study at any point during participation. The site principal investigator may terminate an individual's participation in the study for reasons outlined below:

- Noncompliance with the study protocol
- Health concerns that prevent required follow-up procedures or interval visits

The site investigators should report participant withdrawals and terminations to study monitors as soon as possible. Subjects who withdraw prior to completion of Visit 2 will be required to return the SONNET 3 (EAS) Audio Processor to receive compensation for Visit 1. Participants who are considered lost-to-follow-up should also be reported to study monitors immediately. Every effort should be made to contact participants lost-to-follow-up and determine the reason for noncompliance. If the SONNET 3 (EAS) is not returned, the subject's clinical audiologist will be made aware so that efforts can be made to retrieve the study device at a clinical follow-up appointment.

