5.4.2 HANDLING OF PARTICIPANT WITHDRAWALS OR TERMINATION

Withdrawn participants will continue to be seen by their clinical audiologist for regular follow-up care, but no additional data will be collected. Participants who sign the informed consent/assent form but do not complete all study intervals may be replaced and will return any study equipment to the site. Baseline data collected on withdrawn subjects who are replaced will not be included in the modified intent-to-treat (mITT) or per population (PP) analysis datasets.

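### The primary endpoint is analysed only on participants who complete Visit 2, so a withdrawal over the processor leaves the denominator and no planned analysis would show it

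*Combined protocol and SAP*

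**What the plan says.** Section 10.3 defines three sets and uses two of them for the primary endpoint.

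- **ITT:** "The intent-to-treat (ITT) population is defined as all enrolled participants including withdrawn participants who have been replaced". No analysis is assigned to it.
- **mITT:** "The modified ITT (mITT) population is defined as all participants who completed Visit 1 and Visit 2".
- **PP:** also requires both visits, plus consistent use of the device and no major deviation.
- **Use:** "Analysis for the primary endpoint will be completed on the mITT and the PP populations".

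The Audio Processor Comparison Survey, the only source of the primary outcome, is given only at Visit 2 (Sections 7.1.1 and 7.2.3). Section 10.4.2 defines p through participants who responded and gives no rule for those without a survey.

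On withdrawal, Section 5.4.2 states: "Participants who sign the informed consent/assent form but do not complete all study intervals may be replaced". It sets no limit by reason. It keeps the baseline data of replaced subjects out of mITT and PP, and says of withdrawn participants that "no additional data will be collected". Section 5.4.1 adds: "The site investigators should report participant withdrawals and terminations to study monitors as soon as possible". It also asks for every effort to learn why participants were lost to follow-up. Section 10.4.5, on adherence and retention, is marked not applicable, so no summary of withdrawals is planned.

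**The concern.** The endpoint asks whether users find the new design better. Someone who gives up on the processor before Visit 2 because of its design has, in effect, answered that question. Under Section 10.3 the answer is not counted, whether or not the person is replaced. Compared with counting that person as not improved, leaving them out can only raise the improved proportion.

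Both planned analyses apply the same completer filter, so their agreement says nothing about withdrawals. The study is open-label and single-arm (Section 4.1), so no control arm would show the selection. At stake is whether a narrow success on 20 participants could rest on who stayed, with nothing in the report to tell the reader so.

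**Working it through.** **Inputs.** Null proportion 0.77, one-sided, significance level 0.05, 20 participants, effect size h=0.36 (Sections 10.2, 10.4.1 and 10.4.2). The plan names no specific test for the primary endpoint, so the exact binomial is used unless stated. The plan has no figure for withdrawals to reproduce. Its 85% power is a separate matter and does not enter here. An improver is a participant with a mean Design score above 3.

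**1. Pass mark.** p-value = P(X ≥ x), with X ~ Bin(n, 0.77). For n=20: 18/20 gives 0.128, 19/20 gives 0.037 and 20/20 gives 0.005. The pass mark is 19/20.

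**2. One exit over the processor, at the threshold.**

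| Case | As planned | Exit counted as not improved |
|---|---|---|
| Exit replaced | 19/20, p=0.037, pass | 19/21, p=0.108, fail |
| Exit not replaced | 18/19, p=0.047, pass | 18/20, p=0.128, fail |

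A continuity-corrected z test gives 0.0498 for 19/20 and 0.114 for 19/21, so the replaced case still reverses. It gives 0.059 for 18/19, so the unreplaced case already fails as planned and nothing reverses. If success is read simply as an observed proportion of at least 77%, the threshold moves but the pattern is the same: 16/20 = 80.0% against 16/21 = 76.2%.

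**3. One exit away from the threshold.** With 20/20 completers improved and one replaced exit, 20/21 gives p=0.030 and still passes. With 17 improved among 20 fitted, 17/20 (0.29), 17/19 (0.153) and, with an improving replacement, 18/20 (0.128) all fail. One exit changes nothing in either case.

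**4. Chance of passing at a true 77%.** Let w be the share of non-improvers who leave and are replaced, with no improvers leaving. The proportion improved among completers is 0.77 / (0.77 + 0.23(1 − w)). The values of w are assumptions.

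- w=0: 0.770, P(X ≥ 19 of 20) = 3.7%
- w=5%: 0.77/0.9885 = 0.779, giving 4.5%
- w=10%: 0.77/0.977 = 0.788, giving 5.5%
- w=20%: 0.77/0.954 = 0.807, giving 8.0%

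The chance reaches 5% at w of about 7.7%. If 5% of improvers leave as well, the values at w=5%, 10% and 20% are 3.7%, 4.6% and 6.8%.

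**5. How often the threshold case comes with an exit.** Take 20 fitted with exactly 18 improved. The effect size implies an alternative of sin²(arcsin√0.77 + 0.18) = 0.901. P(exactly 18 of 20) is 0.0910 at 0.77 and 0.2852 at 0.901. At least one of the two non-improvers must also leave, with probability 1 − (1 − w)².

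- w=5%: 0.0975. Joint: 0.0910 × 0.0975 = 0.9%; 0.2852 × 0.0975 = 2.8%.
- w=10%: 0.19. Joint: 0.0910 × 0.19 = 1.7%; 0.2852 × 0.19 = 5.4%.

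With replacement these are upper limits, because a replacement must also be an improver.

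**The case against.** Early exits over design may be few. Follow-up is 2 to 4 weeks. After Visit 2 the participant may keep or return the device (Section 2.3.2), and someone who withdraws earlier must return it to be paid for Visit 1 (Section 5.4.1). A participant who stops wearing the processor but attends Visit 2 stays in mITT. The number lost could also be recovered as ITT minus mITT. All of this stands and limits the size of the problem. It does not supply an analysis of those who leave.

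A reader might go further than the documents allow in three ways.

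- **That the protocol foresees withdrawal over design.** Section 2.3.1 does say that participants who "wish to stop using the SONNET 3 (EAS) (EAS) Audio Processor before study completion may withdraw from the study at any time", but the sentence follows a remark about technical failure or suboptimal fitting. It shows that the exit route exists, not that design is the expected reason.
- **That the threshold case is common.** The 28.5% chance of exactly 18 improved leaves out the exit. With it, the probability is about 1% to 5% at the assumed rates.
- **That the deciding population must be replaced by one that counts only design-related exits as failures.** That denominator would depend on how one open-label site codes reasons, which is a subjective step of its own. The calculated effect does not justify it.

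**Conclusion.** The gap is real: both primary sets are completer sets, replacement is allowed whatever the reason, and the set that keeps replaced withdrawals is not analysed. Its effect is conditional. One exit reverses the conclusion only at the threshold, and the unreplaced reversal also depends on which test is used.

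A reader might infer serious inflation of the false-positive rate. The documents do not support that. They give no withdrawal rate, and at assumed rates of 5% or 10% of non-improvers leaving, the chance of a false pass is 4.5% or 5.5% against 3.7% without exits. Larger inflation needs much higher exit rates, which nothing in the plan suggests. These figures assume the exact test, full replacement and no improvers leaving. The point justifies a sensitivity analysis and transparent reporting, not a new primary population.

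**What to change.** - **Section 10.3:** keep mITT as the primary set. Prespecify a sensitivity analysis of the primary endpoint on all participants fitted with SONNET 3 at Visit 1, including those later replaced. Use the Visit 2 Design score where it exists and count every withdrawal before Visit 2 as not improved. State that a primary success that does not hold in this analysis will be reported as sensitive to withdrawals.
- **Sections 5.4.2 and 10.4.5:** report the number, timing and reason for all withdrawals and replacements.

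The cost is wording in three sections and, if the case report form does not already record the reason for withdrawal, one field. No visits or participants are added. The downside is that the sensitivity result may look less favourable than it should, because some who leave for unrelated reasons might have scored above 3. The reported reasons let a reader judge that. The rule should be set before any results are seen.

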10.4 DESCRIPTION OF STATISTICAL METHODS

10.4.1 GENERAL APPROACH

Continuous variables will be summarized using mean, median, inter-quartile range, minimum, and maximum values. Categorical variables will be summarized using counts and percents. Testing of the primary endpoint will be done at the 0.05 level of significance.

10.4.2 ANALYSIS OF THE PRIMARY EFFECTIVENESS ENDPOINT

The proportion of participants reporting design superiority with SONNET 3 (EAS) on the APCS will be calculated for the primary endpoint. The participant's responses to the Design subsection questions will be averaged and the proportion of participants who rated >3 on average will be compared to the hypothesized proportion of 77%. The statistical hypothesis for the primary endpoint is defined as:

$$H_0: p < 0.77$$

$$H_1: p \geq 0.77$$

where p is the proportion of participants who responded with a mean score of >3.

10.4.3 ANALYSIS OF THE SECONDARY ENDPOINT(S)

All endpoints will be summarized using descriptive statistics outlined in Section 10.4.1. Descriptive statistics will be compared across intervals and audio processor type.

10.4.4 SAFETY ANALYSES

Not applicable

10.4.5 ADHERENCE AND RETENTION ANALYSES

Not applicable

10.4.6 BASELINE DESCRIPTIVE STATISTICS

Baseline demographics will be summarized using mean, median, inter-quartile range, minimum, and maximum values. Categorical variables will be summarized using counts and percents.

10.4.7 PLANNED INTERIM ANALYSES

No interim analysis will be conducted for this study.

10.4.8 ADDITIONAL SUB-GROUP ANALYSES

If sample size permits, results of the secondary endpoints will be stratified by age and existing audio processor model.

10.4.9 MULTIPLE COMPARISON/MULTIPLICITY

Not applicable

10.4.10 TABULATION OF INDIVIDUAL RESPONSE DATA

Individual responses on the Audio Processor Comparison Survey and the Audiologist Survey will be summarized separate from group analysis.

10.4.11 EXPLORATORY ANALYSES

Not applicable

10.5 MEASURES TO MINIMIZE BIAS

This study utilizes a paired design where participants act as their own control. This reduces bias by accounting for within participant variability.

